6.3 Secondary Endpoints

- Progression free survival defined as time in months from the date of first study treatment to the date of disease progression or death from any cause, whichever comes first. Overall survival (OS) is defined as time in months from the date of first study treatment to the date of death. All patients who receive at least one dose of nivolumab and have had their disease re-evaluated will be included in the secondary analyses of PFS and OS.
- Clinical Benefit Rate at 6 and 12 months (CBR, defined as CR + PR + Stable Disease (SD)) in patients with advanced progressive adenoid cystic carcinoma treated with nivolumab and ipilimumab using RECIST v1.1.
- To assess the efficacy of the regimen according to ORR, CBR, PFS, and in the above population using immune-related response criteria (irRECIST) criteria.⁴⁵

NU Study Number: NU 16N03
BMS Study Number: CA 209-802

- The number, frequency, and severity of adverse events will be collected from the time of consent until 12 weeks after study treatment to evaluate safety of nivolumab in patients with advanced progressive adenoid cystic carcinoma. Adverse events will follow National Cancer Institute Common Terminology Criteria for Adverse Events (CTCAE) version 4.03
- Overall survival defined as time in months from the date of first study treatment to the date of death.

6.4 Definitions

Evaluable for toxicity. All patients will be evaluable for toxicity from the time of their first treatment with nivolumab and or ipilimumab.

Evaluable for objective response. Only those patients who have received at least one dose of therapy, and have had their disease re-evaluated will be considered evaluable for response. These patients will have their response classified according to the definitions stated below.

6.5 Disease parameters

Measurable disease. Measurable lesions are defined as those that can be accurately measured in at least one dimension (longest diameter to be recorded) as ≥ 20 mm (≥ 2 cm) by chest x-ray or as ≥ 10 mm (≥ 1 cm) with CT scan, MRI, or calipers by clinical exam (such measurements must be clearly documented). All tumor measurements must be recorded in millimeters (or decimal fractions of centimeters).

Malignant lymph nodes. To be considered pathologically enlarged and measurable, a lymph node must be ≥ 15 mm (≥ 1.5 cm) in short axis when assessed by CT scan (CT scan slice thickness recommended to be no greater than 5 mm [0.5 cm]). At baseline and in follow-up, only the short axis will be measured and followed.

Non-measurable disease. All other lesions (or sites of disease), including small lesions (longest diameter <10 mm [<1 cm] or pathological lymph nodes with ≥ 10 to <15 mm [≥ 1 to <1.5 cm] short axis), are considered non-measurable disease. Bone lesions, leptomeningeal disease, ascites, pleural/pericardial effusions, lymphangitis cutis/pneumonitis, inflammatory breast disease, and abdominal masses (not followed by CT or MRI), are considered as non-measurable.

Note: Cystic lesions that meet the criteria for radiographically defined simple cysts should not be considered as malignant lesions (neither measurable nor non-measurable) since they are, by definition, simple cysts.

‘Cystic lesions’ thought to represent cystic metastases can be considered as measurable lesions, if they meet the definition of measurability described above. However, if non-cystic lesions are present in the same patient, these are preferred for selection as target lesions.

Target lesions. All measurable lesions up to a maximum of 2 lesions per organ and 5 lesions in total, representative of all involved organs, should be identified as target lesions and recorded and measured at baseline. Target lesions should be selected on the basis of their size (lesions with the longest diameter), be representative of all involved organs, but in addition should be those that lend themselves to reproducible repeated measurements. It may be the case that, on occasion, the largest lesion does not lend itself to reproducible measurement in which circumstance the next largest lesion, which can be measured reproducibly should be selected. A sum of the diameters (longest for non- nodal lesions, short axis for nodal lesions) for all target lesions will be calculated and reported as the baseline sum diameters. If lymph nodes are to be included in the sum, then only the short axis is added into the sum. The baseline sum diameters will be used

NU Study Number: NU 16N03
BMS Study Number: CA 209-802

as reference to further characterize any objective tumor regression in the measurable dimension of the disease.

Non-target lesions. All other lesions (or sites of disease) including any measurable lesions over and above the 5 target lesions should be identified as non-target lesions and should also be recorded at baseline. Measurements of these lesions are not required, but the presence, absence, or in rare cases unequivocal progression of each should be noted throughout follow-up.

6.6 Response Criteria – RECIST v1.1

6.6.1 Evaluation of target lesions

Complete Response (CR): Disappearance of all target lesions. Any pathological lymph nodes (whether target or non-target) must have reduction in short axis to <10mm.

Partial Response (PR): At least a 30% decrease in the sum of the diameters of target lesions, taking as reference the baseline sum diameters.

Progressive Disease (PD): At least a 20% increase in the sum of the diameters of target lesions, taking as reference the smallest sum on study (this includes the baseline sum if that is the smallest on study). In addition to the relative increase of 20%, the sum must also demonstrate an absolute increase of at least 5 mm (0.5 cm). (Note: the appearance of one or more new lesions is also considered progressions).

Stable Disease (SD): Neither sufficient shrinkage to qualify for PR nor sufficient increase to qualify for PD, taking as reference the smallest sum diameters while on study.

6.6.2 Evaluation of Non-Target Lesion

Complete Response (CR): Disappearance of all non-target lesions and normalization of tumor marker level. All lymph nodes must be non-pathological in size (<10 mm [<1 cm] short axis).

Non-CR/Non-PD: Persistence of one or more non-target lesion(s) and/or maintenance of tumor marker level above the normal limits.

Progressive Disease (PD): Appearance of one or more new lesions and/or unequivocal progression of existing non-target lesions. Unequivocal progression should not normally trump target lesion status. It must be representative of overall disease status change, not a single lesion increase.

Although a clear progression of “non-target” lesions only is exceptional, the opinion of the treating physician should prevail in such circumstances, and the progression status should be confirmed at a later time by the review panel (or Principal Investigator).

6.6.3 Evaluation of best overall response

The best overall response is the best response recorded from the start of the treatment until disease progression/recurrence (taking as reference for progressive disease the smallest measurements recorded since the treatment started). The patient's best response assignment will depend on the achievement of both measurement and confirmation criteria. Responses will be assessed using CT scans or magnetic resonance imaging according to standard RECIST 1.1 criteria in order to assess disease progression. These criteria will also allow for patients who experience an initial disease flare, and as some patients who will have a delayed response may experience an initial disease flare, we will allow patients to continue receiving nivolumab beyond progression (see section 4.4).

6.6.4 Duration of response

Duration of overall response: The duration of overall response is measured from the time measurement criteria are met for CR or PR (whichever is first recorded) until the first date that recurrent or progressive disease is objectively documented (taking as reference for progressive disease the smallest measurements recorded since the treatment started).

The duration of overall CR is measured from the time measurement criteria are first met for CR until the first date that progressive disease is objectively documented.

Duration of stable disease: Stable disease is measured from the start of the treatment until the criteria for progression are met, taking as reference the smallest measurements recorded since the treatment started, including the baseline measurements.

6.7 Immune-related RECIST (irRECIST)

Immune-related complete Response (irCR): complete disappearance of all lesions (whether measurable or not, and no new lesions)

Immune-related partial Response (irPR): decrease in tumor burden $\geq 30\%$ relative to baseline.

Immune-related progressive Disease (irPD): increase in tumor burden $\geq 20\%$ relative to nadir (minimum recorded tumor burden)

Confirmation by a repeat, consecutive assessment no less than 4 weeks from the date first documented

Immune-related stable Disease (irSD): not meeting criteria for irCR or irPR, in absence of irPD

6.8 Evaluable patients

All patients who receive at least one dose of nivolumab will be considered evaluable for the toxicity endpoints.

All patients who receive at least one dose of nivolumab and have a radiologic evaluation of disease are evaluable for efficacy endpoints.

7.0 ADVERSE EVENTS

This study will be conducted in compliance with the Data Safety Monitoring Plan (DSMP) of the Robert H. Lurie Comprehensive Cancer Center of Northwestern University (please refer to NOTIS for additional information). The level of risk attributed to this study requires High Intensity Monitoring, as outlined in the [DSMP](#). In addition, the study will abide by all safety reporting regulations, as set forth in the Code of Federal Regulations.

7.1 Adverse Event Monitoring

Adverse event data collection and reporting, which are required as part of every clinical trial, are done to ensure the safety of subjects enrolled in the studies as well as those who will enroll in future studies using similar agents. Adverse events are reported in a routine manner at scheduled times during a trial (see Section 5 for time points). In addition, certain adverse events must be reported in an expedited manner to allow for optimal monitoring and patient safety and care.

All patients experiencing an adverse event, regardless of its relationship to study drug, will be followed until:

- the adverse event resolves or the symptoms or signs that constitute the adverse event return to baseline;
- any abnormal laboratory values have returned to baseline;
- there is a satisfactory explanation other than the study drug for the changes observed; or
- death

7.2 Definitions & Descriptions

7.2.1 Adverse Event

An adverse event (AE) is any untoward medical occurrence in a patient receiving study treatment and which does not necessarily have a causal relationship with this treatment. An AE can therefore be any unfavorable and unintended sign (including an abnormal laboratory finding), symptom, or disease temporally associated with the use of an experimental intervention, whether or not related to the intervention.

Recording of AEs should be done in a concise manner using standard, acceptable medical terms. In general, AEs are not procedures or measurements, but should reflect the reason for the procedure or the diagnosis based on the abnormal measurement. Preexisting conditions that worsen in severity or frequency during the study should also be recorded (a preexisting condition that does not worsen is not an AE). Further, a procedure or surgery is not an AE; rather, the event leading to the procedure or surgery is considered an AE.

If a specific medical diagnosis has been made, that diagnosis or syndrome should be recorded as the AE whenever possible. However, a complete description of the signs, symptoms and investigations, which led to the diagnosis should be provided. For example, if clinically significant elevations of liver function tests are known to be secondary to hepatitis, "hepatitis" and not "elevated liver function tests" should be recorded. If the cause is not known, the abnormal test or finding should be recorded as an AE, using appropriate medical terminology (e.g/ thrombocytopenia, peripheral edema, QT prolongation).

7.2.2 Severity of AEs

All adverse events will be graded according to the NCI Common Terminology Criteria for Adverse Events (CTCAE) version 4.03. The CTCAE v4.03 is available at <http://ctep.cancer.gov/reporting/ctc.html>

If no CTCAE grading is available, the severity of an AE is graded as follows:

NU Study Number: NU 16N03
BMS Study Number: CA 209-802

- Mild (grade 1): the event causes discomfort without disruption of normal daily activities.
- Moderate (grade 2): the event causes discomfort that affects normal daily activities.
- Severe (grade 3): the event makes the patient unable to perform normal daily activities or significantly affects his/her clinical status.
- Life-threatening (grade 4): the patient was at risk of death at the time of the event.
- Fatal (grade 5): the event caused death.

7.2.3 Serious Adverse Events (SAEs)

All SAEs, regardless of attribution, occurring from time of signed informed consent, through 100 days after the last administration of study drug, must be reported upon discovery or occurrence.

An SAE is defined in regulatory terminology as any untoward medical occurrence that:

- **Results in death.**
If death results from (progression of) the disease, the disease should be reported as event (SAE) itself.
- **Is life-threatening.**
The patient was at risk of death at the time of the event; it does not refer to an event that hypothetically might have caused death if it were more severe.
- **Requires *in-patient hospitalization or prolongation of existing hospitalization* for ≥ 24 hours.**
- **Results in *persistent or significant disability or incapacity*.**
- **Is a *congenital anomaly/birth defect*.**
- Is associated with an overdose.
For purposes of this trial, an overdose will be defined as any dose exceeding the prescribed dose for nivolumab or ipilimumab by 20% over the prescribed dose. No specific information is available on the treatment of overdose of nivolumab or ipilimumab. In the event of overdose, nivolumab should be discontinued and the subject should be observed closely for signs of toxicity. Appropriate supportive treatment should be provided if clinically indicated. If an adverse event(s) is associated with ("results from") the overdose of a BMS product, the adverse event(s) is reported as a serious adverse event, even if no other seriousness criteria are met.
If a dose of BMS's product meeting the protocol definition of overdose is taken without any associated clinical symptoms or abnormal laboratory results, the overdose is reported as a non-serious Event of Clinical Interest (ECI), using the terminology "accidental or intentional overdose without adverse effect."
All reports of overdose with and without an adverse event must be reported within 24 hours to the Sponsor and within 2 working days hours to BMS Global Safety.
- **Is an *important medical event*.**

Any event that does not meet the above criteria, but that in the judgment of the investigator jeopardizes the patient, may be considered for reporting as a serious adverse event. The event may require medical or surgical intervention to prevent one of the outcomes listed in the definition of "Serious Adverse Event".

All grade 3 or 4 infusion reactions should be reported within 24 hours to the study QAM and reported as an SAE if it meets the criteria. Infusion reactions should be graded according to NCI CTCAE (Version 4.03) guidelines.

For example: allergic bronchospasm requiring intensive treatment in an emergency room or at home; convulsions that may not result in hospitalization; development of drug abuse or drug dependency.

Progression of the cancer under study is not considered an adverse event unless it results in hospitalization or death.

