4.0 TREATMENT PLAN

4.1 Overview

[figure not shown]
Nivolumab and ipilimumab combination will be administered intravenously until disease progression or intolerable toxicity. Nivolumab will be given at 240mg over 30 minutes (-5 / +15 minutes) every 2 weeks starting with Cycle 1 Day 1 for the first 16 weeks (1 cycle = 12 weeks). Starting with Cycle 2 Day 29, nivolumab will be given at 480mg IV over 60 minutes (-10 / +15 minutes) every 4 weeks. Ipilimumab will be given at 1mg/Kg every 6 weeks starting with Cycle 1 Day 1 over approximately 90 minutes (-5 / +15 minutes). On days when both nivolumab and ipilimumab are administered, nivolumab should be given first, followed by ipilimumab about 30 minutes after completion of nivolumab. Patients will be assessed for response every 12 weeks (± 7 days). Note: Please refer to section 4.4 for patients who may continue treatment after initial progression.

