4.3.3 Treatment of Nivolumab or Ipilimumab-related infusion reactions

Since both nivolumab and ipilimumab contain only human immunoglobulin protein sequences, it is unlikely to be immunogenic and induce infusion or hypersensitivity reactions. However, if such a reaction were to occur, it might manifest with fever, chills, rigors, headache, rash, pruritus, arthralgias, hypotension, hypertension, bronchospasm, or other allergic-like reactions.

Treatment recommendations are provided below and may be modified based on local treatment standards and guidelines, as appropriate:

NCI CTCAE Grade	Treatment	Premedication at subsequent dosing
Grade 1 Mild reaction; infusion interruption not indicated; intervention not indicated	Remain at bedside and monitor subject until recovery from symptoms.	The following prophylactic pre-medications are recommended for future infusions: 
 • Diphenhydramine 50 mg (or equivalent) and/or • Acetaminophen 325 to 1000 mg at least 30 minutes before additional nivolumab or ipilimumab administrations
Grade 2 Moderate reaction requires therapy or infusion interruption but responds promptly to symptomatic treatment [eg, antihistamines, non-steroidal anti- inflammatory drugs, narcotics, corticosteroids, bronchodilators, IV fluids]; prophylactic medications indicated for < 24 hours	Stop the nivolumab/ipilimumab infusion, begin an IV infusion of normal saline, and treat the subject with diphenhydramine 50 mg IV (or equivalent) and/or acetaminophen 325 to 1000 mg; Remain at bedside and monitor subject until resolution of symptoms. Corticosteroid and/or bronchodilator therapy may also be administered as appropriate. If the infusion is interrupted, then restart the infusion at 50% of the original infusion rate when symptoms resolve; if no further complications ensue after 30 minutes, the rate may be increased to 100% of the original infusion rate. Monitor subject closely. If symptoms recur, then no further nivolumab will be administered at that visit.	For future infusions, the following prophylactic pre-medications are recommended: 
 • Diphenhydramine 50 mg (or equivalent) and/or • Acetaminophen 325 to 1000 mg should be administered at least 30 minutes before nivolumab or ipilimumab infusions. If necessary, corticosteroids (up to 25 mg of SoluCortef or equivalent) may be used.

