Grades 3 or 4 Severe reaction, Grade 3: prolonged [ie, not rapidly responsive to symptomatic medication and/or brief interruption of infusion]; recurrence of symptoms following initial improvement; hospitalization indicated for other clinical sequelae [eg, renal impairment, pulmonary infiltrates]. Grade 4: Life-threatening; pressor or ventilatory support indicated	Immediately discontinue infusion of nivolumab/ipilimumab infusion. Begin an IV infusion of normal saline and treat the subject as follows: Recommend bronchodilators, epinephrine 0.2 to 1 mg of a 1:1000 solution for subcutaneous administration or 0.1 to 0.25 mg of a 1:10,000 solution injected slowly for IV administration, and/or diphenhydramine 50 mg IV with methylprednisolone 100 mg IV (or equivalent), as needed.	No subsequent dosing

NCI CTCAE Grade	Treatment	Premedication at subsequent dosing
	
Subject should be monitored until the Investigator is comfortable that the symptoms will not recur. Nivolumab or ipilimumab will be permanently discontinued. Investigators should follow their institutional guidelines for the treatment of anaphylaxis. Remain at bedside and monitor subject until recovery of the symptoms
 
In case of late-occurring hypersensitivity symptoms (eg, appearance of a localized or generalized pruritus within 1 week after treatment), symptomatic treatment may be given (eg, oral antihistamine or corticosteroids)
	

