7.4.3.3 Reporting to BMS

All SAE reports (including death by any cause), regardless of attribution will be reported within 24 hours to BMS Global Safety (using the NU CRO SAE Form and referencing the BMS study number, CA 209-802). The assigned study coordinator will facilitate all reporting to BMS Global Safety and email QA a copy of the report upon completion. BMS Global Safety can be notified at:

Email Address: [contact]
[contact]

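### The overdose action and the Grade 2 infusion-reaction recurrence sentence name only nivolumab in a two-drug regimen, and an overdose that is an SAE has two reporting limits to the supplier

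*Combined protocol and SAP*

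**What the plan says.** **Overdose (Section 7.2.3).** The definition covers both drugs: "an overdose will be defined as any dose exceeding the prescribed dose for nivolumab or ipilimumab by 20% over the prescribed dose". The action that follows names one: "In the event of overdose, nivolumab should be discontinued and the subject should be observed closely for signs of toxicity". An adverse event that results from an overdose is to be reported as an SAE. An overdose without symptoms or abnormal laboratory results is a non-serious event of clinical interest. All overdose reports, with or without an adverse event, are due "within 24 hours to the Sponsor and within 2 working days hours to BMS Global Safety".

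**SAE reporting to the supplier (Section 7.4.3.3).** "All SAE reports (including death by any cause), regardless of attribution will be reported within 24 hours to BMS Global Safety".

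**Infusion reactions (Section 4.3.3).** The Grade 2 row opens with both drugs: "Stop the nivolumab/ipilimumab infusion, begin an IV infusion of normal saline". It allows a restart at half rate, and then says: "If symptoms recur, then no further nivolumab will be administered at that visit". The Grade 3/4 row includes "recurrence of symptoms following initial improvement" in its description of Grade 3. It stops the infusion of either drug and allows no subsequent dosing.

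**Order and schedule (Sections 4.1 and 4.2).** When both drugs are given on the same day, "nivolumab should be given first, followed by ipilimumab about 30 minutes after completion of nivolumab". Table 1 puts ipilimumab on Days 1 and 43 of every cycle. Nivolumab falls on Days 29 and 57 in the second part of Cycle 2, and on Days 1, 29 and 57 from Cycle 3.

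**Discontinuation (Sections 4.3.2 and 4.7).** When a physician stops treatment for a suspected drug-related side effect, Section 4.3.2 stops the drug to which the effect is attributed, or both if attribution is not possible. Neither section mentions overdose.

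**The concern.** These are the plan's written instructions for two acute dosing events in a two-drug regimen, and at the key step each names one drug. Ipilimumab is dosed by weight, with adjustment after a weight change of 10% or more (Section 4.2.2). Its dose therefore depends on a patient-specific calculation, and a dose above the overdose limit is a foreseeable event. Section 11.7 requires the study to be conducted as the protocol describes except in an emergency, so sites have reason to take the wording literally. Read that way, sites facing the same event could act differently on treatment. A single serious report could also be on time under one section and late under another.

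**Working it through.** The plan gives no figure to reproduce for the first two parts, so the check sets the sections side by side. Only the reporting limits involve arithmetic.

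**1. Overdose action**

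| Situation | Section 7.2.3 | Section 4.3.2 | Section 4.7 |
|---|---|---|---|
| Nivolumab overdose | Nivolumab discontinued; duration not stated | Overdose not listed | Overdose not listed |
| Ipilimumab overdose, no symptoms | Nivolumab discontinued; silent on ipilimumab | Attribution rule not triggered, as there is no side effect to attribute | Overdose not listed |
| Ipilimumab overdose with symptoms, physician decides to stop | Nivolumab discontinued; silent on ipilimumab | Stop the attributed drug, or both | Ends treatment if the event is unacceptable |

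The second row is a gap: no other section gives an overdose instruction. The third row is a mismatch: the two sections can give different instructions for one patient. The investigator-judgment item in Section 4.3.2 does not close the gap, because it refers to the risk of continued nivolumab dosing only.

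**2. Recurrence of a Grade 2 infusion reaction**

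- Cycle 1, Days 1 and 43, and every later Day 1: both drugs are given. By the time ipilimumab is running, nivolumab is complete.
- Day 43 from Cycle 2 on: ipilimumab is scheduled and nivolumab is not. This is one of the two ipilimumab visits in each of those cycles.

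In both situations, if symptoms recur during ipilimumab, withholding further nivolumab at that visit restricts nothing. The row is therefore inconsistent with its own first instruction, which covers both infusions.

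The adjacent rows also overlap. Symptoms that settle, allow a restart and then return fit the Grade 2 recurrence sentence, whose effect ends with the visit. They also fit the recurrence feature listed under Grade 3, whose effect is that dosing ends. Section 4.3.2 likewise requires discontinuation for a Grade 3 drug-related infusion reaction of any duration. Section 4.3.3 does not say which row takes a recurrence after restart.

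**3. Reporting limits to the supplier's safety unit**

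The limits conflict only for an overdose with a resulting adverse event, because Section 7.4.3.3 applies to SAEs. The inputs are 24 hours (Section 7.4.3.3) and 2 working days (Section 7.2.3, where the unit is garbled). Assumption: a Monday-to-Friday week without holidays.

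- Site aware early in the week (for example Monday): 2 working days is about 2 × 24 = 48 hours. Difference: 48 − 24 = 24 hours.
- Site aware on Thursday or Friday: the weekend adds 2 × 24 = 48 hours, so 48 + 48 = 96 hours. Difference: 96 − 24 = 72 hours.

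The two limits for the same event and recipient differ by about 24 to 72 hours.

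**The case against.** Much of the plan works against a harsh reading, and several of these points stand.

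- **Symptomatic overdose is partly covered elsewhere.** Section 4.3.1 delays both drugs for toxicity that meets its criteria, Section 4.3.2 discontinues by attribution, and Section 4.7 ends treatment for unacceptable adverse events. This stands, and it leaves the asymptomatic ipilimumab overdose as the main gap. It does not remove the disagreement between Sections 7.2.3 and 4.3.2.
- **The Grade 3/4 row already deals with recurrence in both drugs.** This stands against any claim that the plan has no means of stopping ipilimumab after a recurrence. It also means that two rows answer the same question differently.
- **The infusion-reaction table is advisory.** Section 4.3.3 allows modification under local standards. That softens the consequence but does not make the rows agree.
- **Reporting within 24 hours satisfies both limits.** This is true, and Section 7.4.3.3 is clear on its face. A site that relies on Section 7.2.3 would still be late under Section 7.4.3.3.

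A reader might infer that an ipilimumab event stops the wrong drug. The documents do not support that as a general statement. For overdose, they show that the rule does not address the drug involved; which drug should be stopped is a clinical decision. For a recurrence during ipilimumab, the sentence stops nothing at that visit.

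A reader might also infer that such a patient would count toward the stage 1 rule of 7 or more among 15. Section 10.2 counts patients withdrawn from the study and Section 4.5 counts patients discontinued. Neither says how stopping one of two drugs counts, and the documents give no overdose frequency, so that consequence is speculative.

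**Conclusion.** The point holds as three wording inconsistencies in safety management and reporting:

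1. The overdose action omits one of the two drugs that its definition covers, can differ from the attribution rule when symptoms occur, and has no stated duration.
2. The Grade 2 recurrence sentence omits one of the two drugs its row covers, has no effect at the visit when the recurrence is during ipilimumab, and conflicts with the Grade 3/4 row.
3. An overdose that is an SAE has two limits to one recipient, about 24 to 72 hours apart under the working-week assumption above.

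The first two rest on the text alone. None of this touches the sample size, the decision boundaries or the error rates of the two-stage design. It is worth correcting because sites would apply these instructions under time pressure, and the correction is cheap. No view is taken here on which clinical instruction or deadline is right.

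**What to change.** In the next amendment the sponsor, with the supplier, should:

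- reconcile Section 7.2.3 with Sections 4.3.2 and 4.7, so that the overdose action addresses each drug the definition covers and states whether it is temporary or permanent;
- reconcile the Grade 2 recurrence sentence in Section 4.3.3 with the rest of its row, with the Grade 3/4 row and with Section 4.3.2, so that a recurrence after restart has one consistent instruction;
- state one deadline to the supplier's safety unit for an overdose that is an SAE, the same in Sections 7.2.3 and 7.4.3.3, and repair the garbled time unit.

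The clinical content of the first two items is for the sponsor to decide. The cost is a few sentences and a cross-check of the sections named, with no added procedures or patients.
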